1.1 STUDY SCHEMA

1.2 SCHEDULE OF EVENTS (SOE)

Study Procedures & Assessments	Visit Schedule									
	Week									
	BL	Intake	1	2	4	13	26	39	52	
Consent	R									
Randomization (when determined eligible)		R								
Interventions (mCPT with or without CRP)										
Massed Cognitive Processing Therapy (mCPT)					1x/day					
Crisis Response Planning (CRP) or Treatment as Usual (TAU)					R					
Booster Sessions										up to 3 over the follow-up year
Adverse Event Reporting		R	R	R	R	R	R	R	R	R
Assessments:	R	R	R	R	R	R	R	R	R	R
1. Demographic and Military Service Characteristics	x									
2. History of Head Injuries Questionnaire + Addendum (HHI+HHI-A)	x									
3. Self-Injurious Thoughts and Behaviors Interview-Revised (SITBI-R)	x I	x* SR	x* SR	x* I						
4. Scale for Suicide Ideation (SSI)	x	x	x	x	x	x	x	x	x	x
5. Interpersonal Needs Questionnaire (INQ)	x					x	x	x	x	x
6. Beck Hopelessness Scale (BHS)	x					x	x	x	x	x
7. Suicide Cognitions Scale-Revised (SCS-R)	x	x	x	x	x	x	x	x	x	x
8. Difficulties with Emotion Regulation Scale-Short Form (DERS-SF)	x					x	x	x	x	x

Abbreviated Title: mCPT+CRP

Version Date: 07/10/25

9. Monetary Choice Questionnaire (MCQ)	x				x	x	x	x
10. Behavioral Inhibition System and the Behavioral Activation System (BIS/BAS)	x				x	x	x	x
11. Clinician Administered PTSD Scale for DSM-5 (CAPS-5) with Selection of Index Events (SOIE)	x							
12. Life Events Checklist (LEC)	x							
13. PTSD Checklist for DSM-5 (PCL-5)**		x	x	x	x	x	x	x
14. Posttraumatic Cognitions Inventory (PTCI-9)		x	x	x	x	x	x	x
15. Satisfaction with Therapy and Therapist Scale – Revised (STTS-R)			x					
16. Cornell Services Index-Short Form (CSI-SF)	x				x	x	x	x
17. PROMIS Computer Adaptive Tests (PROMIS- CATs)		x	x	x	x	x	x	x
18. Clinical Global Impression (CGI)			x	x				
19. Ecological Momentary Assessment (EMA)			6x/day for 28 days					
20. Fitbit			for 28 days					
21. Qualitative Interview				x				
All activities are for research. * “Since your last assessment” version ** “In the past week” version for all assessments. I = Interview; SR =Self-report								

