19. Ecological Momentary Assessment (EMA). This study will utilize EMA to assess participants' behaviors, mood, and social context in real time in participants' natural environments. Positive and negative mood state will be assessed using 15 items to assess affect, some drawn from the Positive and Negative Affects Scale (PANAS; Watson et al., 1988). Social context will include researcher-developed items to assess who participants are with and perceived closeness to other people. Suicidal ideation will be assessed using a sum score of items assessing various facets of ideation including wish to live, wish to die, suicidal intent, feeling that life is not worth living, and thoughts about suicide. Consistent with best-practice recommendations (Conner & Lehman, 2012), we will employ a mixture of fixed time-based sampling and experience sampling. A fixed time-based survey will be administered every morning to assess the occurrence of variables during the preceding night or prior day, and experience sampling will be used to deliver five standardized surveys, distributed quasi-randomly during each day (<5 minutes to complete). The protocol for these prompts draws from items from a battery that measures: 1) select items assessing current positive and negative affect and rumination; 2) items measuring suicidal ideation and behavior; 3) items measuring substance use; 4) behavioral and contextual factors that can impact risk/resilience for our outcomes of interest (i.e., stressful situations, social engagement), 5) sleep characteristics, and 6) crisis response plan use.

Please note that while all of the possible 96 questions are being submitted for regulatory reviews, a selection of questions 1-50 will be administered each morning during EMA and a selection of questions 1-46 (starting on page 7) will be administered the other times throughout the day.

Participants will respond to EMA prompts through their smartphone. Participants will be trained to complete the EMA procedures by study staff who will lead participants through a training demo to ensure that participants understand how and when to answer questions through EMA. EMA prompts will be randomly delivered throughout the day, with no scheduled differences between weekend and weekday prompts. To offset participant reactivity, question sets will be administered in a random

Abbreviated Title: mCPT+CRP

Version Date: 07/10/25

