9.2.1 BIOSPECIMEN EVALUATIONS N/A

9.2.2 SAMPLES FOR GENETIC/GENOMIC ANALYSIS N/A

9.3 SAFETY ASSESSMENTS N/A

Study assessments that will be done to ensure inclusion and exclusion criteria are outlined as part of the inclusion and exclusion criteria in Section 6 (Study Population) and Section 9 (Study Assessments and Procedures).

Baseline suicide-specific measures are reviewed by a member of the study staff to determine if any additional assessment or intervention is warranted.

Safety Assessment Specific to EMA: Participants will be instructed to complete the EMA surveys in a safe place and during a time when they can briefly (< 5 minutes) stop what they are doing to answer the EMA questions. Participants will have up to an hour to respond to the questions to allow them time to respond to the EMA prompts in a safe place.

Risk of suicide might be a concern for some participants. Although suicidal ideation is a risk factor for suicidal behavior, most people who think about suicide do not act on these thoughts. Additionally, studies have demonstrated that repeated assessment does not cause or lead to suicidal thoughts/behaviors. As such, the current protocol itself is not likely to increase participant's risk for suicide. Nonetheless, suicide risk might naturally change throughout the course of the study, and we have developed a detailed protocol to address safety concerns that might arise. For suicidality reported during EMA prompts, our research team has successfully conducted a number of studies assessing suicidality via EMA among high-risk patients, including both adolescents and adults.

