window (up to 42 EMA surveys per participant) for each participant: stability (i.e., the autocorrelation of scores over time), severity (i.e., mean score across all responses), and variability (i.e., the root mean square successive difference [RMSSD] across all responses). Each change index will be entered as an independent variable into a linear regression model predicting pre-post change in SSI score and a binary logistic regression model predicting follow-up suicidal behavior. To evaluate the specificity of these findings to the two weeks of active treatment, we will expand these analyses to include all 5 weeks of planned EMA data collection (i.e., 1 week prior to treatment start, 2 weeks of treatment, 2 weeks after treatment completion). This approach will allow us to distinguish treatment-specific patterns from more general patterns that signal treatment response and treatment relapse. **Power Analysis:** Power calculations for H3 were conducted using G*Power 3.1.9.2 (for suicidal ideation) and PROC POWER in the SAS 9.4 software (for suicide attempts). For the linear regression model, N=150 yielded 80% power to detect a medium effect ($R^2=0.06$) and for the binary logistic regression, N=150 provided >80% power to detect an odds ratio=1.5, assuming a conservative 20% of participants attempts suicide during follow-up.

Exploratory Research Question 1: Which subjective, objective, and treatment-related factors are most useful for predicting treatment response (i.e., change in severity of suicidal ideation) and treatment relapse (i.e., follow-up suicidal behavior)?

We will use the same analytic approach described for H3 but extend the analyses to all other variables assessed via EMA (i.e., positive and negative affect, negative thinking, and maladaptive behaviors) and Fitbit (i.e., physical activity, sleep quality). We will construct a series of models to determine which variables (and combination of variables) maximize the variance explained in pre-post change in SSI score and follow-up suicidal behavior. **Power Analysis:** Power calculations for RQ1 were conducted using G*Power 3.1.9.2. Assuming our model includes no more than 6 predictor variables, N=150 yielded 80% power to detect R^2 increases of 0.06-0.08 associated with each additional predictor variable.

Hypothesis 4: More frequent CRP use will be correlated with reductions in suicide attempts and suicidal ideation.

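### With no spacing rule, the H3 stability index partly tracks how many EMA prompts were answered; the variability index is also shifted, but its link with completion is weak when people differ

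*Protocol*

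**What the plan says.** Under Hypothesis 3, Protocol 10.4.2 reduces each participant's ideation ratings during massed CPT to three numbers. One is the mean. The other two are "stability (i.e., the autocorrelation of scores over time" and "variability (i.e., the root mean square successive difference [RMSSD] across all responses". Each is a predictor in a linear model for change in SSI and in a logistic model for later suicidal behavior. RQ1 carries the same approach to the other EMA variables.

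The section gives no lag, no rule for overnight pairs or pairs that span a missed survey, no minimum number of responses and no adjustment for completion.

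The schedule is in 9.2.1, item 19: "A fixed time-based survey will be administered every morning to assess the occurrence of variables during the preceding night or prior day", while "experience sampling will be used to deliver five standardized surveys, distributed quasi-randomly during each day". Section 9.3 adds that "Participants will have up to an hour to respond to the questions". Section 6.6.2 pays from 75% of weekly surveys (32 of 42), with a higher tier at 90% (38 of 42), so incomplete responding is expected. The missing-data methods in 10.4.1 are aimed at the longitudinal results, not at these person-level summaries.

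**The concern.** RMSSD and autocorrelation compare neighbouring observations, so their values depend on how far apart the neighbours are. If an index is computed over whatever responses exist, a missed prompt joins two surveys that were not scheduled next to each other. Where serial correlation is positive and fades with time, the longer gap weakens the correlation and enlarges the difference. Two participants with identical ideation dynamics then get different values because one answered fewer prompts.

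Aim 2 seeks early markers of response and relapse, and section 4.2 says they should support decision tools for clinicians. If completion is itself related to outcome, an apparent instability marker could partly be a count of missed surveys.

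**Working it through.** **The plan's survey count.** Section 10.4.2 describes the two-week "window (up to 42 EMA surveys per participant) for each participant". Section 1.2 has "6x/day for 28 days", and 6 × 14 = 84. The figure 42 fits one week at six per day, or two weeks at three per day. This is a separate inconsistency; both schedules are covered below.

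**Missed prompts, closed form.** Assume a stationary series with correlation ρ between successive scheduled prompts, each answered independently with probability c. The gap between answered prompts is geometric, so the expected correlation of successive responses is

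r = cρ / (1 − (1 − c)ρ),

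and RMSSD changes by the factor √[(1 − r)/(1 − ρ)]. For ρ = 0.7 and c = 0.5: r = 0.35/0.65 = 0.538, and the factor is √(0.462/0.300) = 1.24.

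| ρ | c = 0.75: r, RMSSD factor | c = 0.50: r, RMSSD factor |
|---|---|---|
| 0.3 | 0.243, 1.040 | 0.176, 1.085 |
| 0.5 | 0.429, 1.069 | 0.333, 1.155 |
| 0.7 | 0.636, 1.101 | 0.538, 1.240 |
| 0.8 | 0.750, 1.118 | 0.667, 1.291 |

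The autocorrelation falls by 0.05 to 0.07 at 75% completion and by 0.12 to 0.17 at 50%.

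**Simulation on the protocol's schedule.** This used a continuous-time autoregressive process, one morning and five quasi-random prompts a day, for 14 days. Clock times, correlations and completion levels are assumptions.

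- Correlation 0.7 at 2.5 hours, completion 100% to 50%: RMSSD 0.88 to 1.06, autocorrelation 0.58 to 0.38.
- Correlation 0.5: RMSSD 1.07 to 1.21 (+13%), autocorrelation 0.39 to 0.21.
- Correlation 0.85: RMSSD 0.65 to 0.84 (+29%), autocorrelation 0.75 to 0.58.
- Correlation 0.7 with measurement noise of SD 0.7: RMSSD rises by only 8%.
- Very slow decay (72 hours) falls outside the main range. RMSSD goes from 0.319 to 0.444 (+39%) without noise and from 1.034 to 1.076 (+4%) with it. The autocorrelation falls by 0.10 and 0.05.
- Three prompts a day, 12-hour decay: RMSSD 0.937 to 1.087 (+16%), autocorrelation 0.487 to 0.277. The conclusion does not depend on which survey count is right.

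**Overnight gaps.** At full completion, with decay times of 3 to 24 hours, using all pairs makes RMSSD 6 to 20% higher and the autocorrelation 0.06 to 0.08 lower than within-day pairs do. Every participant has these nights.

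**Link with completion (40 to 100%).**

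- Identical dynamics for everyone: correlation with completion −0.32 to −0.63 for RMSSD and +0.42 to +0.55 for the autocorrelation.
- People differing in amplitude and decay time (log-SD 0.5): −0.05 to −0.16 for RMSSD and +0.28 to +0.41 for the autocorrelation. A further set of runs gave about 0 to −0.2 and +0.2 to +0.4.

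**False positives.** Suppose the outcome relates to completion at r = 0.3 but not to ideation dynamics, with N = 150 and 200 simulated trials. The Monte Carlo standard error at 5% is √(0.05 × 0.95/200) = 1.5 percentage points. The autocorrelation is significant in 33%, 23.5% and 19% of trials at log-SD 0, 0.3 and 0.5. RMSSD is significant in 29%, 6% and 4%.

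**Which restriction works.** With correlation 0.7 at 2.5 hours, the autocorrelation over all within-day pairs still falls from 0.65 to 0.53 at 50% completion. With consecutively scheduled same-day pairs it goes from 0.65 to 0.63. The correlation with completion then stays within ±0.07 in one set of runs and at most about 0.15 in another.

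**The case against.** The strongest reply is that 10.4.2 names indices and leaves their construction to a statistical analysis plan, which was not available here. That has force for the autocorrelation: the words about all responses are attached to the mean and to RMSSD, not to it, and no lag is stated. It has less force overall, because the protocol does commit to a form for RMSSD and to a plain autocorrelation on a schedule that is uneven by design.

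Several stronger readings are tempting, and the documents do not support them:

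- **Both indices are equally confounded.** This holds only if everyone shares the same dynamics. When people differ widely in amplitude, RMSSD's link with completion is weak and its false-positive rate is near nominal.
- **The shift is about two standard deviations.** That divides an RMSSD shift of 0.17 by a sampling SD of 0.084, with no true variation between people. Against a between-person SD near 0.6 it is about 0.3 SD.
- **Overnight gaps create the confounding.** They are common to all participants. They change the level and meaning of the indices, not their relation to completion.
- **Good responders at floor drop out of the stability model.** A constant series has no autocorrelation, but nothing shows such series will be common. The score sums several items, and entry requires recent ideation or suicidal behavior.
- **The morning survey contaminates the ratings.** Only a selection of items is asked then, and the list is not shown. Whether its ideation items look back is unknown.

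It is also fair that 50% completion lies below the lowest pay tier. No analysis floor is stated, however, and effects at 75% are smaller but not zero. The r = 0.3 between completion and outcome is an assumption.

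**Conclusion.** The concern holds in a limited form. Without a spacing rule, and given positive serial correlation, missed prompts lower the autocorrelation by about 0.1 to 0.2 at 50% completion and about 0.04 to 0.08 at 75%. They raise RMSSD by about 6 to 29% at 50%, depending on the serial correlation and measurement noise, with the very slow processes shown above outside these ranges. The stability index therefore partly measures EMA completion, with a correlation of about +0.2 to +0.4 even when people differ. For RMSSD this is a minor issue unless people are alike in amplitude. If ideation had no serial correlation, the effect would vanish.

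The reach is Hypothesis 3 and RQ1. H1, H2 and the randomised comparison do not use these indices.

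**What to change.** In 10.4.2, for Hypothesis 3 and RQ1, compute both indices only from pairs of surveys scheduled consecutively on the same day and both answered. Exclude overnight pairs and pairs that span a missed prompt. Exclude the morning survey too if its ideation items are retrospective. Restricting to within-day pairs without the consecutive requirement is not enough. Enter the number of completed surveys as a covariate in the H3 and RQ1 regressions, at least as a sensitivity analysis.

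This is a cheap improvement: wording and some programming, with no new data. The price is precision. Six surveys a day give 14 × 5 = 70 eligible pairs at full completion. With independent responses about 70 × 0.75² = 39 remain at 75% and 70 × 0.5² = 17.5 at 50%, against 62 and 41 when all successive responses are paired. Dropping the morning survey leaves 14 × 4 = 56, or 14 at 50%. Indices for participants with low completion will be noisier.

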10.4 STATISTICAL ANALYSES

10.4.1 General Approach

Prior to statistical analyses, data will be screened to assess the need for scale transformations (e.g., log, reciprocal) to normalize distributions or reduce variance heterogeneity. The study design is a two-arm randomized clinical trial with a superiority hypothesis (i.e., CRP superior to usual care). Analyses will use survival analysis and mixed effects regression with repeated measures. Follow-up assessment data will be collected from participants even if they drop out of therapy early. The primary focus will be on

Abbreviated Title: mCPT+CRP

Version Date: 07/10/25

group differences over time. All hypotheses will be two-sided at the $\alpha=.05$ level. Little's MCAR test will be used to determine if data are missing at random (Li, 2013; Little et al., 2002) and random effects pattern-mixture modeling will be used to determine if missingness influences longitudinal results (Hedeker & Gibbons, 1997; Little, 1993). The principal statistical software to be used is SAS 9.4 supplemented with SPSS, R, and MPlus.

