We will sum the number of EMA responses during which participants endorsed the use of their CRP (and safety plan), such that higher values indicate more frequent intervention use. This count variable will be entered into a Cox regression model predicting time to suicide attempt and a linear regression model predicting change in SSI score to assess the correlation of intervention use with, respectively, follow-up suicidal behavior and severity of suicidal ideation. We will construct separate models for each treatment group. To test the specificity of our findings to CRP, we will repeat these analyses with CPT homework completion, also assessed during EMA and calculated as the sum of positively endorsed EMA responses, entered as a covariate. **Power Analysis:** The power analysis for H4 mirrors the power analysis for H3 above.

Exploratory Research Question 2: Which treatment components and design features do participants find most helpful for reducing suicidal ideation and attempts?

We will use descriptive statistics of participant characteristics, chi-squared tests, and Pearson correlations (where applicable) to explore relationships among personal experiential themes, group experiential themes, and participant characteristics. **Power Analysis:** Recommendations for minimum sample size in qualitative studies using IPA typically range from 2-25 participants, depending on the homogeneity that exists within participants' lived experience (Alase, 2017; Smith et al., 1999). Because we plan to interview all enrolled participants, our sample size will be more than adequate.

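### H3 and RQ1 name no treatment-group term and appear to pool the arms, so an early ideation marker can partly reflect the CRP effect; the bias is modest and one covariate removes it

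*Protocol*

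**What the plan says.** Section 10.4.2 of the Protocol defines three indices of EMA-rated ideation over the two weeks of massed CPT for H3: stability (autocorrelation), severity (mean) and variability (RMSSD). It then says "Each change index will be entered as an independent variable into a linear regression model predicting pre-post change in SSI score", and adds a binary logistic model for follow-up suicidal behavior. No treatment-group term, stratification or per-arm fit is named. Both power statements use the whole randomised sample; for the logistic model, "N=150 provided >80% power to detect an odds ratio=1.5, assuming a conservative 20% of participants attempts suicide during follow-up".

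RQ1 asks "Which subjective, objective, and treatment-related factors are most useful for predicting treatment response" and answers it this way: "We will use the same analytic approach described for H3 but extend the analyses to all other variables assessed via EMA", plus Fitbit variables. Its power statement begins "Assuming our model includes no more than 6 predictor variables, N=150 yielded 80% power".

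The neighbouring analyses do deal with arm. H2 enters treatment group, time and their interaction. For H4 the Protocol says "We will construct separate models for each treatment group". Section 10.4.1 sets the test level: "All hypotheses will be two-sided at the $\alpha=.05$ level".

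**The concern.** By the Protocol's own account, arm acts on both sides of the H3 severity regression.

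- **Timing.** The randomised suicide-risk intervention is given at intake, one to two weeks before the first CPT session (section 7.1.2). The H3 window is the later two weeks of CPT, so the marker is measured after CRP.
- **Marker.** The pilot reported a larger fall in ideation under CRP within one week, at the CPT midpoint (section 4.3).
- **Outcomes.** The H2 power calculation assumes SSI differences of 4 points at midpoint and 2 at treatment end. H1 is powered for hazard ratios of 0.50 to 0.75.

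If CRP works as hypothesised, CRP participants have lower severity, larger SSI improvement and fewer attempts. Pooling then creates an association in H3's predicted direction even for a marker that says nothing once the arm is known. Section 4.2 wants these markers to inform clinicians' decision tools. A marker that partly encodes which plan the patient received would carry over poorly to a clinic where everyone receives the same one.

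H3's planned specificity check, extending the EMA window to before and after CPT, does not separate the two. EMA starts at the intake appointment (section 9.2.1), where CRP is also delivered.

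**Working it through.** **Inputs from the Protocol.** N = 150, taken as 75 per arm; two-sided alpha 0.05; 15% attrition (from the H1 power statement); SSI difference 2 at treatment end; hazard ratio 0.50 to 0.75 with 30 to 50% attempting in usual care; H3 linear effect R² = 0.06.

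**Assumptions.** The Protocol gives neither the SD of SSI change nor the shift in the EMA index. SD is taken from 4.3 to 10, where 4.3 is the value at which a simple two-group comparison of 2 points would have 81% power at N = 150. The marker shift is 0.5 SD, with 0.8 SD as a larger case.

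**Step 1: the plan's own figure.** Noncentral F with λ = N·R²/(1 − R²). One predictor at 150 × 0.85 ≈ 128 gives 81.0%; two tested predictors at N = 150 give 78.9%. Either matches the stated 80%. One predictor at the full 150 gives 86.7%. A single arm gives 57.9% (n = 75) or 51.2% (n = 64), so the stated power is consistent only with using both arms together.

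**Step 2: SSI change, marker unrelated to outcome within each arm.** With equal arms and standardised shifts dm (marker) and dy (outcome),

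r = (dm·dy/4) / √[(1 + dm²/4)(1 + dy²/4)].

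For dm = 0.5 and dy = 2/7.8 = 0.256: r = 0.0321/√(1.0625 × 1.0164) = 0.031; λ = 150·r²/(1 − r²) ≈ 0.14; rejection 6.6% (6.4% at n = 128).

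| SD of SSI change | dy | r | Rejection, N = 150 |
|---|---|---|---|
| 10 | 0.20 | 0.024 | 6.0% |
| 7.8 | 0.26 | 0.031 | 6.6% |
| 4.3 | 0.47 | 0.055 | 10.3% |

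**Step 3: attempts.** The CRP proportion is 1 − (1 − p)^HR; for example, p = 40% and HR 0.50 give 1 − √0.60 = 22.5%. Unadjusted logistic regression was run on 20,000 simulated trials per row, with the outcome depending on arm only.

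| Usual care | HR | CRP | Shift 0.5 SD: rejection (OR per SD) | Shift 0.8 SD: rejection (OR per SD) |
|---|---|---|---|---|
| 30% | 0.75 | 23.5% | 5.0% (1.04) | 6.1% (1.06) |
| 40% | 0.75 | 31.8% | 5.6% (1.04) | 6.2% (1.06) |
| 50% | 0.75 | 40.5% | 5.6% (1.05) | 6.9% (1.07) |
| 30% | 0.50 | 16.3% | 7.4% (1.09) | 10.6% (1.14) |
| 40% | 0.50 | 22.5% | 8.1% (1.10) | 12.5% (1.15) |
| 50% | 0.50 | 29.3% | 8.6% (1.11) | 15.5% (1.17) |

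Reading a 50% reduction as half the proportion (40% v 20%) gives about 9% and OR 1.12 at a 0.5 SD shift.

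**Step 4: with an arm term.** Rejection returns to 4.5 to 5.0% in every row of the step 3 table, and to 4.8 to 5.3% in simulated linear models. Linear power for R² = 0.06 given arm stays at 86.7% (N = 150) or 81.0% (n = 128).

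**The case against.** **Pooling is inferred.** Saying that each index is entered does not say that nothing else is, and covariate lists for secondary models are often left to an SAP, which is not shown here. H4 has its own reason to split by arm, because it counts use of two different tools. This stands as a limit on certainty. Even so, the Protocol specifies these models and powers them on both arms without mentioning arm.

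**H3 is about prediction.** A crude pooled association is a valid prognostic statement, and a marker with no within-arm association is a worst case, given the rationale that lowering ideation lowers behavior. This also stands. What the pooled result cannot show is that the marker adds information once the form of care is known.

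**Stronger readings that the documents do not support:**
- *A larger bias for SSI change.* Using the 4-point difference at SD 7.8 gives r = 0.06 and about 11%. That is the midpoint value; H3's outcome is pre-post change, and the stated difference at treatment end is 2.
- *A larger bias for attempts.* Carrying over the pilot's 73% reduction, for example 40% v 12%, gives about 15% at a 0.5 SD shift. Section 4.3 derives that figure from counts of attempts, 1 − (7/41)/(21/33) = 73.2%, whereas the logistic model uses the proportion of participants with an attempt. The scenario also lies outside the planned hazard ratios.
- *The same bias for every index.* The Protocol says nothing about CRP shifting autocorrelation, RMSSD, or Fitbit activity and sleep.
- *RQ1 holds no treatment variable.* Its listed variables include none, but EMA also records crisis response plan use and CPT homework (section 9.2.1 and the H4 text), so the text is ambiguous.

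**Conclusion.** The concern holds, at modest size. H3 and RQ1 as written name no arm term and appear to pool the arms. For the severity index, the Protocol's own expectations make arm a common cause of marker and outcome, in the direction H3 predicts. For stability, variability and the Fitbit variables this holds only if CRP shifts them.

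At a 0.5 SD marker shift, the false-positive rate for a marker with no within-arm association is about 6 to 10% for SSI change. For attempts it is about 6 to 9% with 40 to 50% attempting in usual care, and 5 to 7% with 30%. The spurious odds ratios of 1.04 to 1.12 per SD are small beside the 1.5 the plan is powered for. At HR 0.50, a 0.8 SD shift takes the attempt figure to about 13 to 15% (11% with 30% in usual care). These results rest on the assumed marker shift and SSI SD, and they vanish if CRP has no effect. This is a free improvement, not a major error.

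**What to change.** In section 10.4.2, add randomised arm as a covariate to every H3 and RQ1 model, linear and logistic, including the extended-window analyses. Report the marker-by-arm interaction descriptively. State that conclusions about early markers rest on the arm-adjusted coefficient; the crude pooled association can be shown beside it. In RQ1 the arm term also supplies part of the treatment-related factors that the question names.

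The cost is one degree of freedom per model and no new data. A covariate is preferable to separate models by arm, which would cut H3 linear power to about 58% (n = 75) or 51% (n = 64). The term should be written in before outcome data are seen.
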